3.0 STUDY SUMMARY

Fortyeight patients (48) with Old World cutaneous leishmaniasis will be randomly allocated to WR 279,396 treatment once a day for 20 days with an optimized polyurethane dressing (occlusion) (24 patients), or without occlusion (24 patients). All

patients will be rescued with the standard of care accepted in Tunisia, if the patient is not cured. The active ingredients of WR 279,396 are two aminoglycosides – paromomycin sulphate (15%) and gentamicin sulphate (0.5%) – in a base (AQIC).

Efficacy will be evaluated in terms of the number of lesions cured at D50 (D1 is the first day of treatment) with no relapse during 3 months post-treatment follow-up. Cure is defined as 100% reepitheliazation without relapse by 3 months.

Tolerance will be evaluated by local adverse reactions and by laboratory signs of systemic events.

In addition to the clinical evaluation of the CL lesions, the following parameters/clinical healing surrogates will be investigated:

- (a) parasite load will be determined in superficial and deep lesional dermis samples at D0 and D10. The mean parasite reduction ratio (parasite load at D10/parasite load at D0) in each group will be compared;
- (b) aminoglycoside concentrations (paromomycin and gentmicin) in superficial and deep infiltrated dermis in each group will be compared

One 4mm punch biopsy of the lesion randomized as explained above will be performed under epicutaneous plus transcutaneous anesthesia at day 0 and one 4 mm punch biopsy at day 10. The biopsy specimen will be divided in two: superficial dermis and deep dermis.

The results from this study will help determine the most practical treatment schedule and will answer questions that are crucial to improve the present treatment regimen with WR 279,396 which is twice a day for 20 days. This will facilitate the management of patients in the field and will help answer FDA questions during the licensing phase of the product.

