8.0 EXPERIMENTAL PLAN

8.1 Trial Design

Fortyeight (48) patients of Old World cutaneous leishmaniasis will be randomly allocated to WR 279,396 treatment once-a-day for 20 days with occlusion (24 patients), without occlusion (24 patients). Patients not cured will be rescued with a conventional treatment accepted in Tunisia as determined by the primary care physician. The active ingredients of WR 279,396 are two aminoglycosides – paromomycin sulphate (15%) and gentamicin sulphate (0.5%) – in a base (AQIC).

Efficacy will be evaluated in terms of the number of lesions cured i.e. percentage of subjects cured at D50 (D1 is the first day of treatment) with no relapse during 3 months post-treatment follow-up. Cure is defined as 100% reepitheliazation without relapse by 3 months. Clinical improvement is defined as \geq 50% but \leq 100% reepitheliazation compared to pre-treatment lesion size at day 50 (\pm 7 days). Lack of clinical improvement at day 50 (\pm 7 days), relapse that is enlargement of the lesion compared to the previous measurement at any time after day 50 (\pm 7 days), or not demonstrating complete clinical response by 3 months will be a clinical failure. Time to cure will also be determined. Toxicity will be evaluated by local adverse reactions, and by laboratory signs of systemic events.

Induration of the lesion, as measured by the ball-pen technique, will be measured at the same time as lesion size. A photograph will be taken concurrently with these measurements to document the procedure and provide a visual record of the induration measurement and lesion size.

In addition to the clinical evaluation of the CL lesions, the following parameters/clinical healing surrogates will be investigated: (a) parasites loads will be determined in superficial and deep lesion dermis at D0 and D10. The mean parasite log-reduction ratio (log parasite load at D10/log parasite load at D0) in each group will be compared; (b) aminoglycoside concentrations in superficial and deep infiltrated dermis in each group will be compared.

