8.2 Trial endpoints

- 1. Primary endpoints: Lesion size and clinical response described as reepithelialization. Lesion size refers to ulcer size only, here, and the rest of the protocol.
- 2. Secondary endpoint: safety and tolerance of WR 279,396.
- 3. Third end point: D0 to D10 Deep Lesion Dermis Parasite Load Reduction Ratio.

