9.0 SAMPLE SIZE AND DATA ANALYSIS

9.1 Sample size calculation

If the cure rate in the WR 279,396 without occlusion group is assumed to be $60\%^1$, and we desire at least a 35% improvement in the cure rate due to occlusion, for alpha=0.05 (1-sided) and beta=0.2, 20 patients under WR 279,396 without occlusion plus 20 patients WR 279,396 with occlusion (40 patients) are required for 1:1 allocation.

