9.2 Efficacy calculations

Data analysis will be undertaken in 3 stages: conception of an electronic database from the questionnaire, data entry and cleaning to insure validity of data and statistical analysis: A database will be written from the CRF. Data entry with a double-check will be performed at the end of the protocol at the Tunisian site with U.S. support. Cleaning of the data base will be insured by comparing data entered to the computer to the information in the source documents. Data analysis will be done by an independent qualified statistician hired in the United States for this phase of the protocol.

The primary criterion for treatment evaluation will be the percentage of patients that demonstrate complete clinical response (all lesions cured or improved) at day 50. The response rate for WR 279,396 groups will be compared by Fisher's Exact test. Time for the ulcer to cure will also be determined and the means will be used to compare the two groups. Results will also be analyzed per cohort (Tegaderm VS no Tegaderm) and the age of the lesion at treatment D0 (\leq 2.5 months of age VS \geq 2.5 months of age).

The secondary efficacy calculation will be the deep lesional dermis parasite load log reduction ratio at Day 10 of treatment with/without occlusion. Mean parasite loads in the two groups, will be compared using student's t tests.

As for all efficacy calculations the data analysis for safety and tolerance of WR 279,396 will be done by a qualified statistician and results between the two groups compared.

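### Section 9.2 compares deep-dermis parasite load by an unadjusted t-test on an outcome defined in several ways; an analysis of covariance of log D10 load on log D0 load is a free gain in precision

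*Protocol*

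**What the plan says.** Section 8.1 plans the measurement at both times: "parasites loads will be determined in superficial and deep lesion dermis at D0 and D10". The timetable in Section 8.17 schedules a biopsy and a parasite load at D0/1 and at D10.

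The outcome built from these measurements is described in different ways:

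- Section 3.0, ratio of raw loads: "The mean parasite reduction ratio (parasite load at D10/parasite load at D0) in each group will be compared".
- Section 8.1, ratio of logs: "The mean parasite log-reduction ratio (log parasite load at D10/log parasite load at D0) in each group will be compared".
- Section 8.2, third endpoint, scale not stated: "D0 to D10 Deep Lesion Dermis Parasite Load Reduction Ratio".
- Section 9.2: "The secondary efficacy calculation will be the deep lesional dermis parasite load log reduction ratio at Day 10 of treatment with/without occlusion". This could mean the log of the ratio (a change in log load) or the ratio of the logs.

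The next sentence of Section 9.2 fixes the test, and it refers to loads rather than to any ratio: "Mean parasite loads in the two groups, will be compared using student's t tests". It names neither a day nor a covariate.

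Section 8.1 gives the arm sizes as "with occlusion (24 patients), without occlusion (24 patients"). Section 9.1 sizes the trial on cure rate alone: "for alpha=0.05 (1-sided) and beta=0.2, 20 patients under WR 279,396 without occlusion" and the same number with occlusion. Section 9.3 describes 1:1 randomisation and states no stratification.

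**The concern.** The D0 load is likely to predict the D10 load, and it is measured before treatment. A two-sample t-test either leaves it out (if D10 loads are compared) or uses it with a fixed weight (if a change or a ratio is compared). Neither removes the association with D0 in general. A change score subtracts the whole of D0, which over-corrects when the correlation is below 1. ANCOVA estimates the weight from the data.

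What is at stake is the precision of the plan's laboratory evidence on whether occlusion strengthens the drug effect in the deep dermis. That evidence bears on the first question in Section 4.0. The trial is small and each patient has two biopsies, so information already collected should be used. The open definition matters as well, because the power of the stated test depends strongly on which outcome is put into it.

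**Working it through.** **The plan's own figure.** The protocol gives no power for parasite load. Its only power figure is for cure: 20 per arm, 60% against 95%, one-sided 5%, 80% power. The exact one-sided Fisher power for those inputs is 80.8%, so that figure reproduces. It says nothing about this endpoint.

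**Inputs.** From the protocol: n = 24 per arm (Section 8.1). Assumed: two-sided 5%; log10 loads with SD 1 at each time; true difference d = 0.7 SD; D0–D10 correlation ρ = 0.5, with range 0.3 to 0.7.

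**Formulae.** Power comes from the noncentral t distribution with noncentrality d / √(2V/n), where V is:

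- D10 log load: V = 1, df = 2n − 2 = 46
- change in log load: V = 2(1 − ρ), df = 46
- ANCOVA: V = (1 − ρ²)(1 + 1/(2n − 4)), df = 2n − 3 = 45

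At ρ = 0.5 the first two both have V = 1, so the noncentrality is 0.7/√(2/24) = 2.42 and the power is 66.1%. For ANCOVA, V = 0.75 × (1 + 1/44) = 0.767, so the noncentrality is 0.7/√(2 × 0.767/24) = 2.77 and the power is 77.3%.

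| ρ | t-test, D10 log load | t-test, log change | ANCOVA |
|---|---|---|---|
| 0.3 | 66.1% | 51.9% | 69.1% |
| 0.5 | 66.1% | 66.1% | 77.3% |
| 0.7 | 66.1% | 86.5% | 90.7% |

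At 20 per arm (Section 9.1) and ρ = 0.5 the figures are 57.8% for either t-test and 69.0% for ANCOVA.

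**The two ratios.** These have no simple formula, so they were simulated (20,000 trials per setting, normal log10 loads with SD 1, mean D0 4 to 6, mean D10 2 to 5, d = 0.7).

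- *Ratio of logs (Section 8.1).* At ρ = 0.5 the t-test has about 72–77% power, against about 77–78% for ANCOVA, a loss of up to about 5 points. Over ρ = 0.3 to 0.7, with mean falls of 1 to 3 log10, the loss runs from about 1 point or less to about 11. A fall from 6 to 2 at ρ = 0.7 gives 12. If the mean load does not fall at all, the ratio behaves much like a change score. With mean 5 at both times, ρ = 0.5 and the effect set so that a D10 t-test has 80% power, the ratio gives 78.5% and ANCOVA 89.0%, a loss of 10.5 points.
- *Ratio of raw loads (Section 3.0).* At ρ = 0.5 the t-test has about 16% power, because the ratio is highly skewed. At ρ = 0.3 it has about 8%, and at ρ = 0.7 about 39%.

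**Error rate with no true difference.** The t-tests on D10 log load, log change and ratio of logs, and ANCOVA, all reject in close to 5% of trials. The t-test on the raw ratio rejects in about 1–2%, so it is conservative.

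**The case against.** The strongest reply is that D0 is already in the outcome. Sections 3.0, 8.1 and 8.2 all define a D0-to-D10 ratio, and the sentence in Section 9.2 just before the t-test names a log reduction ratio. A reader who takes the t-test sentence alone might infer that the plan ignores D0 altogether. The documents do not support that: it follows only if mean loads is read literally as D10 loads. This part of the reply stands. It does not remove the point, because referring an outcome to baseline is not the same as adjusting for baseline, and ANCOVA had the highest power in every setting examined.

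A reader might also infer that chance imbalance in D0 load makes the comparison invalid. It does not. Allocation is randomised, so the unadjusted test holds its error rate. In a single trial of this size the D0 means will differ by chance: the standard error of that difference is √(2/24) = 0.29 SD, so a gap above 0.3 SD in either direction occurs in about 30% of trials. That variation is already counted in the t-test's wider interval. It costs efficiency and does not cause bias.

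Two further replies carry weight. The endpoint is supportive: it is third in Section 8.2, and the study is titled a pilot. Covariate adjustment is also often settled in an analysis plan, which is not available here. However, the protocol does not leave this open. It names a specific test, and it gives the outcome in versions that do not agree.

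**Conclusion.** The point holds as one of efficiency and definition. Section 9.2 fixes a valid but less efficient test, for an outcome that the protocol does not define in one way.

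A loss of 10 points of power should not be quoted without qualification. It is about right (11 points) for a t-test on D10 log load or log change at ρ = 0.5 and 0.7 SD. For the ratio of logs, the definition closest to the wording of Sections 8.1 and 9.2, it is up to about 5 points at ρ = 0.5. Across ρ = 0.3 to 0.7 it is about 1 to 11 points, and it depends on the assumed mean loads. The collapse to about 16% applies only if the raw ratio of Section 3.0 is tested. Section 9.2 speaks of a log ratio, so that is the least likely reading, but the text does not exclude it.

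The correlation, SD, effect size and mean loads are all assumptions, and the simulations ignore any detection limit of the assay. The ranking does not depend on one choice of these values: ANCOVA was best throughout.

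**What to change.** In Section 9.2, name one outcome, log10 deep-dermis parasite load at D10. Replace the t-test by a linear model with arm as factor and log10 deep-dermis load at D0 as covariate. Report the adjusted difference between arms with its 95% confidence interval; on the log10 scale this back-transforms to a ratio of geometric mean loads. Align Sections 3.0, 8.1 and 8.2 so that all describe this outcome. The same model for superficial dermis is optional, since Section 9.2 names only the deep dermis.

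The change is to wording only. It needs no further patients, visits or biopsies, uses a baseline that is already collected, and costs one degree of freedom.

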9.3 Treatment randomization codes

The study will be randomized 1:1 occlusion/non occlusion. The randomization list will be generated by the Department of Epidemiology of Institut Pasteur of Tunis using a sequential numbers from 1 to 50.

¹ In Colombia, WR279396 without occlusion gave a 60% cure rate (30% above the placebo cure rate).

9.4 Missing or unused data

The Case Report Form was designed to capture the same result multiple times making it very hard to have missing data. In addition, check lists are common throughout the protocol. Nevertheless, if data is missing the PIs will try their best to obtain the missing data. Unused data will not be published. If a subject is lost to follow-up prior to day 50, the data will not be included in the analysis. If a subject is lost to the study between day 50 and the third month follow-up, the PIs will have the option to use the data with remarks.

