2.0 BACKGROUND

An analysis of the data from the recent WR 279,396 study (HSRRB Log # A-9768.1) indicates that by day 50, cure rate was 91.8% in the treatment group and 73.2% in controls ($x^2 = 5.60$, p= 0.017) and complete cure response was 95.8% among the former versus 75% among the latter ($x^2 = 8.04$, p= 0.004). The global healing rate is already much higher than the previous (placebo) 25% healing rate in the same area using the same evaluation criteria (Ben [name] 95). The occlusive dressing used during the ongoing trial may have positively influenced the healing rate, by enhancing drug diffusion into the deep dermis and accelerating the reepithelialization process. The practicability of polyurethane adhesive dressings was not perfect however. Local reactions (mild pain, redness and edema) was noticed among 22 patients (11 among the treatment group (22.4%) and 11 among controls (28.6%), NS. Although no patient stopped drug applications, topical treatment might be improved by simplifying the regimen. WR 279,396 without occlusion was superior to placebo in a Colombian Phase 2 study (Soto 02) making it the reference schedule. No tolerance problems were observed in this trial.

The Office of the Surgeon General, United Sates Army represented by USAMMDA holds the IND for WR 279,396 and will continue the development of the product through a commercial pharmaceutical partner in order to obtain licensure by the FDA.

Thus, this Phase 2 study is to determine whether WR 279,396 with occlusion (a polyurethane dressing) is more effective than WR 279,396 without occlusion. Furthermore, a consistent difference in efficacy will be necessary to justify the relatively lower tolerance and higher cost of an occlusive dressing, and this study will help determine which form of dressing should be used.

Extensive objective and subjective local tolerance data will also be captured during this trial, as well as surrogate markers (parasite loads and aminoglycosides concentration in the deep dermis) that may help to determine the optimal number and duration of treatments. Finally, this study, which will be conducted from October 2005 through March 2007, will bridge the time gap between the 2004 Phase 2 study and the planned 2006 Phase 3 study. This will serve to keep the clinical team in Tunisia active and ready to start the next trial should that study be necessary.

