Major questions remain to be addressed in order to accurately decide the appropriate arms of the pivotal Phase 3 study are: (a) is occlusion necessary and useful; and (b) would administration of WR 279,396 once-a-day for 20 days be as effective as twice a day for 20 days.

Any new treatment regimen in cutaneous leishmaniasis should be amenable to local health system constraints so our intent is to develop the simplest and shortest treatment schedule that will support easily application to children and soldiers in rural remote areas. A consistent difference of efficacy will be necessary to justify the relatively lower tolerance and higher cost of occlusive dressing. Decreasing the number of applications of the test drug will not only simplify the treatment but decrease the number of times that dressing is applied, thus diminishing the number of AEs triggered by peeling off the Tegaderm.

This study bridges the ongoing Phase 2 study that ended follow-up on November 2004 and the start of the Phase 3 trial.

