8.12 Definition of responses using clinical criteria

Lesions will be measured in two perpendicular directions, and photographs will be taken, prior to therapy, at the end of therapy, and at 50 days, 3 months, (D1 being the first day of treatment). Physically identifying features if present will be hidden in photographs. Patients will be identified by initials and not by name. Because the trial can't be blinded, clinical evaluation at D50 will be performed by an independent physician ([name]) unaware of the occlusion process. Patients will be asked not to inform the evaluating physician if the lesion was covered.

Efficacy will be evaluated in terms of percentage of patients cured or improved at D50 (D1 is the first day of treatment) with no relapse during 3 months post-treatment follow-up.

1. Cure: 100% reepithelialization without relapse by 3

months.

2. Clinical improvement: $\geq 50\%$ but $\leq 100\%$ reepitheliazation compared to pre-

treatment lesion size at day 50 (\pm 7 days).

3. Clinical failure: a. Lack of clinical improvement at day 50 (\pm 7 days)

after the beginning of treatment.

b. Relapse that is enlargement of the lesion compared to the previous measurement at any time after day 50

 $(\pm 7 \text{ days}).$

c. Not demonstrating complete clinical response by 3

months (i.e. not being cured by 3 months).

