8.14 Criteria for Early Withdrawal from the Study

Any one of the following criteria will be considered sufficient to cause the withdrawal of the patient from the study.

- 1. Adverse effects (particularly those listed in section 7.10.2) reported by the patient or medical personnel that in the opinion of the principal investigator pose a serious risk to the patient.
- 2. Clinical failure or relapse. Patients who require re-treatment for failure or relapse will be removed from the protocol and treated with the standard of care, probably 0.5 3.0 ml of Glucantime intralesionaly once per week for a maximum of 5 weeks or in case of

multiple lesions (n≥4) Glucantime at 20 mg SbV/kg /day for a maximum of 20 days) or the attending physician drug of choice.

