8.15 Concomitant medications

If concomitant medical problems occur, medications that are possibly effective against cutaneous leishmaniasis (antimony, amphotericin B, pentamidine, injectable paromomycin, fluconazole, ketoconazole, allopurinol) will only be used as a measure of last resort and this patient will be withdrawn from the protocol.

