18.0 ROLES AND RESPONSIBILITIES OF THE STUDY PERSONEL

Principal Investigators: Responsible for protocol adherence and execution, passage of protocol through Tunisian protocol committee, tie-breaking blinded assessment of lesion changes in patients, data integrity, applying for and receiving approval for any modifications to the protocol or consent form in Tunisia, training of associate investigators, ensuring safety of the volunteers, and reporting of any adverse events.

Subinvestigators: Responsible for protocol adherence and execution, passage of protocol through Tunisian protocol committee, tie-breaking blinded assessment of lesion changes in patients, data integrity, applying for and receiving approval for any modifications to the protocol or consent form, ensuring safety of the volunteers, managing and reporting of any adverse events, briefing potential volunteers, obtaining proper informed consent, determining study eligibility based on screening data and the exclusion criteria, and recording all observations and data in the individual subject records.

Medical Monitors: Responsible to provide medical care and monitoring of research subjects for conditions that may arise during the conduct of the study. The medical monitor will review all serious adverse events and all unexpected adverse events (per ICH definitions) associated with the protocol and provide an unbiased written report of the event within 10 calendar days of the initial report. At a minimum, the medical monitor will comment on the outcomes of the adverse event (AE) and relationship of the AE to the test

article. The medical monitor will also indicate whether he/she concurs with the details of the report provided by the study investigator.

Coordinator Consultant and Study Monitor: Assures overall coordination of the study and protocol writing in collaboration with the PIs. Assures the study is conducted under cGCP in collaboration with the QC unit at USAMMDA. Uses his expertise in the product and previous experiences in Phase 1 and Phase 2 studies with WR 279,396 in support the Principal Investigators. Reviews weekly Reports and Summary Study Reports and communicates with the PIs accordingly. As a member of the Product Development Team keeps lines of communication open with the Product Managers and update other members of the Product Development Team in the United States by phone. Reviews and updates for the product managers the Annual Reports and Final reports.

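### Section 9.4 drops patients lost before day 50 and leaves later losses to investigator choice; both rules can bias the randomised comparison

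*Protocol*

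**What the plan says.** Protocol section 9.4 has one rule for each period of loss.

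- Before day 50: "If a subject is lost to follow-up prior to day 50, the data will not be included in the analysis".
- Between day 50 and month 3: "the PIs will have the option to use the data with remarks". It does not say when the data would be used, who records the reason, or whether the choice is made before allocation and outcome are known.

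Other sections bear on these rules:

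- **Withdrawal.** Section 8.14: "Patients who require re-treatment for failure or relapse will be removed from the protocol". It also allows withdrawal for adverse effects that the principal investigator judges a serious risk. Section 8.15, on other drugs active against leishmaniasis: "this patient will be withdrawn from the protocol". Neither section says whether such a patient counts as lost under 9.4.
- **Blinding.** Section 8.12: "Because the trial can't be blinded, clinical evaluation at D50 will be performed by an independent physician". Only that physician, at that visit, is described as unaware of occlusion. Section 18.0 nevertheless gives the principal investigators and subinvestigators a role in "tie-breaking blinded assessment of lesion changes in patients".
- **Tolerance.** Section 2.0: "a consistent difference in efficacy will be necessary to justify the relatively lower tolerance and higher cost of an occlusive dressing". Section 7.0 repeats the expectation.
- **Endpoint.** Section 9.2 sets the primary criterion at day 50. Sections 3.0, 8.1, 8.4 and 8.12 define cure as complete re-epithelialisation with no relapse by 3 months.

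**The concern.** Randomisation protects a comparison of everyone who was allocated. Deleting patients because their outcome is missing replaces that with a comparison of those who stayed. If the arms lose different numbers of patients, and those lost differ in prognosis from those who stay, the cure rates are no longer comparable. The protocol expects one arm to be less well tolerated, so unequal loss is a plausible risk.

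The second rule adds discretion. Where cure requires month-3 status, a patient lost after day 50 has no settled outcome, and the investigators decide whether that patient enters the denominator. Under the day-50 criterion of section 9.2 the patient already has a result, and the same wording would let that observed result be discarded. In an open trial of 48 patients, one or two such decisions can move the test across its threshold.

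**Working it through.** **Inputs.** 24 patients per arm (3.0, 8.1, 8.4); Fisher's exact test (9.2); one-sided alpha 0.05, 60% versus 95% cure, 80% power (9.1). The protocol gives no expected loss for this trial. Reference values are 2 of 92 = 2.2% in the earlier Old World trial, and 5 of 56 = 8.9% non-evaluable active lesions in Colombia (both 6.4.1).

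**Step 1: the plan's own figure.** Power is the sum of Bin(a; n, 0.60) × Bin(b; n, 0.95) over all outcomes with one-sided Fisher p ≤ 0.05. It is 77.8% at n=19 and 80.8% at n=20, so the stated 20 per arm reproduces. At 24 per arm it is 89.0%.

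**Step 2: what deletion does, in the protocol's own data.** In Colombia, active cure is 33/56 = 58.9% with all lesions counted and 33/51 = 64.7% with non-evaluable lesions removed (+5.8 points). Placebo is 4/17 = 23.5% and 4/12 = 33.3% (+9.8 points). If the non-evaluable lesions were uncured, removing them helps the arm that lost more.

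**Step 3: bias and false-positive rate.** Let p be the true cure rate in both arms and l the fraction of an arm lost, all uncured. The completers' cure rate is p/(1−l). With p=0.75, 24 per arm and one-sided Fisher at 0.05:

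| Loss, occlusion v control | Completers' rates | Bias | Rejection, enumerated (simulated) |
|---|---|---|---|
| 2.2% v 2.2% | equal | 0 | 2.5% (2.7%) |
| 4.4% v 0% | 0.75/0.956 = 78.5% v 75% | +3.5 points | 4.5% (4.6%) |
| 15% v 5% | 0.75/0.85 = 88.2% v 0.75/0.95 = 78.9% | +9.3 points | 10.3% (10%) |
| 15% v 0% | 88.2% v 75% | +13.2 points | 18.0% (17–18%) |

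Counting the same losses as not cured gives no bias and 2.6% rejection in every row, because all those lost are uncured by assumption. At p=0.60, 15% v 5% gives 0.60/0.85 − 0.60/0.95 = +7.4 points and about 7.5% rejection.

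The direction depends on who is lost. If all losses were cured patients, 15% v 5% at p=0.75 would give (0.60/0.85) − (0.70/0.95) = 70.6% − 73.7% = −3.1 points, against occlusion.

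**Step 4: how many patients it takes.** One-sided Fisher, occlusion v control:

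- Early loss: 20/24 v 14/24 gives p=0.055. Deleting one uncured occlusion patient, 20/23 v 14/24, gives p=0.030; deleting two, 20/22 v 14/24, gives p=0.013.
- Late loss: 21/24 v 15/24 gives p=0.047. Choosing not to use one late-lost patient who was cured at day 50, 20/23 v 15/24, gives p=0.055.

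**The case against.** **The loss rates are assumed, and the high ones are extreme.** With 25% of patients uncured, losing 15% and 5% of the arms means losing 60% of occlusion failures and 20% of control failures. Nothing in the protocol supports those values. The earlier Old World trial lost 2 of 92, and section 2.0 reports that no patient stopped applications. This stands as a limit on the size. It does not show that loss will be equal here, because both arms of that trial were occluded (6.5.4.2).

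**A reader might infer that the bias must favour occlusion.** That needs more loss under occlusion and losses that are mostly uncured. The protocol states lower tolerance, not tolerance-driven loss. In Colombia pain was more frequent on active treatment (55% v 33%, 6.5.4.1), yet non-evaluable lesions were more frequent on placebo (5/17 v 5/56). Only a conditional direction is supported.

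**A reader might infer that sections 8.14 and 8.15 and Appendix A feed failures into the deletion rule.** Section 8.12 defines failure at day 50 or later, so a patient removed for failure or relapse normally has a day-50 result. Appendix A ends treatment, not follow-up. Section 9.4 speaks of loss to follow-up and does not say that withdrawn patients are included. What remains is an unresolved status for patients withdrawn before day 50 for adverse effects or other antileishmanial drugs.

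**A reader might say that unblinded investigators choose the primary denominator.** That they know the allocation is a fair inference from section 8.12, but section 18.0 assigns them a blinded task, so the two must be reconciled. The option sets whether a late-lost patient counts toward cure by 3 months. Under section 9.2 the day-50 result already exists, and the fault is that it could be set aside. Nor does the option turn a cured patient into a failure: the contrast is 21/24 with 20/23, not with 20/24 (p=0.097 against 15/24).

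**Conclusion.** The point holds as a stated rule that can give a wrong answer. Section 9.4 fixes a completers-only analysis before day 50 and an uncontrolled choice afterwards, and no section sets an analysis of all randomised patients.

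The bias ranges from none at 2.2% loss in each arm, through +3.5 points at 4.4% v 0%, to +9 to +13 points under heavy selective loss, where the nominal 5% test rejects about 10% to 18% of the time. These figures assume that every lost patient is uncured and that true cure is 75% in both arms. Bias toward occlusion is the likelier direction only if poor tolerance drives loss of uncured patients.

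If loss stays near the earlier trial's level, average bias will be small, but one deleted or discarded patient can still decide significance at this sample size. This should be fixed; it does not by itself invalidate the trial.

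**What to change.** Replace section 9.4 with wording to this effect:

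1. The primary analysis includes all randomised patients in their assigned arm. A missing day-50 outcome, or another antileishmanial treatment before the evaluation, counts as not cured.
2. One fixed rule, with no investigator choice, covers losses after day 50. For example, missing month-3 status counts as not cured, with day-50 status carried forward as a sensitivity analysis.
3. The completers analysis is kept as a sensitivity analysis.

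Also state whether patients withdrawn under 8.14 and 8.15 count as lost, reconcile 8.12 with the blinded role in 18.0, and say whether the primary outcome is the day-50 criterion of 9.2 or cure without relapse by 3 months.

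The change is wording, but it has a price. Cure rates fall, and power for 60% v 95% at 24 per arm drops from 89.0% with no loss to 84.7% at 2.2% loss and 71.0% at 8.9% loss, if loss is equal in both arms and unrelated to outcome (both rates multiplied by 1−loss). At those two loss rates 80% power needs 22 and 30 per arm. If only the occlusion arm loses 8.9%, power falls to 57.0%. Counting missing as not cured penalises whichever arm loses more, so it would favour occlusion if control lost more; the sensitivity analyses are needed for that reason.
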